325 a home programme (described below). Monitored Home Programme (HO) (standard care):
326 Approximately 2 weeks post-surgery, patients allocated to HO will attend 1 group-based
327 exercise session at Fairfield, Sutherland or Campbelltown Hospitals where the home
328 programme will be rehearsed and exercises individualised as per extant co-morbidities.
329 Patients will be encouraged to attend a 2nd class within the first 2-8 post-operative weeks to
330 encourage exercise progression and discuss any ongoing issues with the therapist. *Patients in*
331 *both groups will receive a booklet (see attached) detailing the home programme, and will be*
332 *permitted to contact the therapist by phone in this period for advice.* Any patient can be
333 reviewed at any time by the therapist within the first 8 weeks of surgery if there are any
334 concerns raised by either the patient or the therapist. All patients will be required to complete
335 a diary detailing programme adherence and healthcare utilisation.^{8,9}

336 Treating therapists will be required to complete a study proforma detailing therapy provided
337 and therapy attendance and any complications.

338 Therapy provided to those who do not consent to participate

339 Patients who do not consent to participate in the study will receive standard care, i.e. the HO
340 programme. Due to unforeseen circumstances, some may be discharged to inpatient
341 rehabilitation.

342

343 3.3. NUMBER OF PARTICIPANTS*

344 A minimum of 140 participants will be assigned to either the HI or HO groups with a
345 minimum of 70 in each group.

- 346 3.4. NUMBER OF CENTRES
347 - There are two recruitment centres and four treatment sites.
348 - Fairfield and Sutherland Hospitals are the recruiting sites. Fairfield, Sutherland
349 and Campbelltown Hospitals will oversee the monitored home programme.
350 - Braeside and Sutherland Hospitals will provide the inpatient rehabilitation.

351 3.5. DURATION
352 The study is expected to take approximately 48 months including 30 months for
353 recruitment, 12 months from enrolment of the last participant, and 6 months for
354 analysis.

355

356 4. PARTICIPANT SECTION

357 4.1. INCLUSION CRITERIA*

- 358 • Undergoing primary unilateral TKR at Fairfield or Sutherland Hospital
- 359 • Having a primary diagnosis of osteoarthritis
- 360 • Willingness to give written informed consent and willingness to participate
361 to and comply with the study.
- 362 • Age 40 years or over

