486 that participants have come through surgery without suffering any relevant adverse
487 outcomes (see exclusion criteria) and are progressing towards discharge. If it is determined

488 that there is a need for rehabilitation at this time, patients are no longer eligible to
489 participate in the study due to exclusion criteria.

490 The University of Sydney Randomisation service will be used for participant randomisation
491 (1:1 ratio). This is a centralised service providing secure, coded randomisation via a
492 telephone. The randomisation service will generate and hold the randomisation schedule.
493 Allocation will be concealed until the point of randomisation. Randomisation will occur as
494 close to the time of intervention as possible, by waiting 3-4 days post-surgery for clearance
495 to participate.

496 Participants will be randomised to one of the two intervention groups using the method of
497 minimisation stratified for age (≤ 70 , >70 y), gender and height.

498

499 **6. SAFETY***

500 6.1. ADVERSE EVENT REPORTING*

501 Adverse events experienced by the patient during the acute period will be monitored to
502 ensure the patient remains eligible for the study. Monitoring will occur via the ward-based
503 physiotherapist who will inform the investigators of the patient progress.

504 Adverse events post discharge from acute care will be monitored, whether they be related or
505 unrelated to the study intervention. This will occur via communication with the
506 physiotherapists providing therapy (inpatient or monitored home programme) and at the
507 follow-up assessments with the patient. Adverse events include any post-surgical
508 complication, falls or instances of greater than expected muscle or joint soreness.

509 If the treating therapist detects a complication, then, as per standard practice, they will
510 advise the treating surgeon and any relevant registrar or GP of their concern and also record
511 this information in the study proforma and patient record. If the patient simply informs the
512 treating therapist about a known complication, then the therapist will record the
513 complication in the study proforma and the patient's record. The study investigator will be
514 informed as soon as possible by the physiotherapist of any complication that the therapist
515 considers may interfere with the patient's capacity to continue with either programme.

516

517 6.2. DATA SAFETY AND MONITORING BOARD

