663 (The HIHO study): study protocol for a randomized controlled trial. *Trials* 2013; 14:432.

664 The study was registered prospectively in April 2012 on a clinical trials registry - U.S.
665 National Institutes of Health Clinical Trials Registry ref: NCT01583153.

666 **eMethods1. Statistical analysis plan**

667

668 **HIHO STATISTICAL ANALYTICAL PLAN (SAP) – JANUARY 2014**

669

670 **Background**

671 HIHO is a 2-armed parallel randomised controlled trial comparing 10 days on inpatient
672 rehabilitation followed by a hybrid home program (usual care) to a hybrid program alone in
673 people who have undergone a TKA. A third observational arm provides the opportunity to
674 assess the effect of preference on the measured outcomes as well as assess generalisability of
675 the randomised cohort.

676 Participants are randomly assigned via a central randomisation process to 1 of 2 arms. A
677 centralised randomisation service will be used for participant randomisation using a 1:1 ratio,
678 providing secure, coded randomisation via telephone. Group allocation, therefore, will be
679 concealed from all parties until the result of the randomisation is known. Participants will be
680 randomised to one of the two intervention groups using the method of minimisation stratified
681 for variables that affect the primary outcome (distance walked in the 6MWT - age (≤ 68 y,
682 >68 y), height (≤ 163 cm, >163 cm), and gender.

683 Participants are followed up by an assessor blind to treatment allocation at 10, 26 and 52
684 weeks.

685 Neither therapists or participants are blind to the intervention received.

686 Different therapists are involved in the delivery of the inpatient and home-based programs.

687 **Data management**

688 Data will be sent by blinded assessors to blinded data entry staff for collation and data entry,
689 with range checks for data values. All databases will be password protected and stored in
690 secure areas. Data will be checked for accuracy against the source documents by the study
691 coordinator after all participants are randomized and then when all participants have had their
692 final follow-up.

693 **Statistical plan**

694 **Outcome measures:** The primary outcome and most secondary outcomes will be measured
695 pre-operatively, at week 10 (the time when the home program formally ceases), and then at 6
696 and 12 months post-randomisation. Assessments will be performed by an observer blinded to

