697 the participants' study allocation.

698 The primary endpoint in this trial is functional mobility at 6 months post-surgery measured
699 using the distance walked during a 6MWT. Seventy participants in each group (140 in total)
700 will provide 80% power at a significance level of 5%, to detect an increase in walking
701 capacity from 400 m to 460 m between the Home and Inpatient groups respectively in the
702 six-minute walk test at six months post-surgery, assuming a SD of 120 m and a drop-out rate
703 of $< 10\%$. With the addition of a second recruitment site, the definitive sample is expected to
704 be approximately 160 participants, allowing us to increase the power of the study.

705 In the absence of data describing the minimum clinically important difference (MCID) for the
706 6MWT, a sub-study is now included to evaluate the MCID/MID for measured mobility in
707 this population.

708 **Descriptive analyses at baseline**

709 Comparability of intervention groups will be investigated at baseline. Descriptive statistics
710 will be presented, including summary statistics of potential confounding variables.

711 **Analyses subsets**

712 Data analysis will be completed using the principle of intention-to-treat (ITT) [1]. We will
713 include all randomised participants regardless of level of compliance with the protocol. The
714 primary outcome variable is distance measured using the outcome of a 6MWT at 26 weeks.

715 Analysis of covariance will be used for this primary outcome, with treatment group as the
716 main study factor and walking distance at baseline, weight, co-morbidities and patient
717 preference as covariates. For participants with a missing outcome measure at 26 weeks, an
718 imputation method will be used [1,2].

719 The secondary outcome variables include the 6MWT at 10 and 52 weeks post-surgery, the 15
720 metre walk test, EQ5D, Oxford Knee Score, KOOS and knee ROM at most post-surgery time
721 points.

722 Mixed model analyses will be used for the continuous variables measured repeatedly at 10,
723 26 and 52 weeks to estimate the treatment group by time effects. These analyses incorporate
724 the missing data that may occur at the follow up occasions. Baseline measurements of the
725 outcome variables, together with factors, such as weight, co-morbidities and patient
726 preference, will be included as covariates. For the binary outcome measured 10, 26 and 52

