727 weeks (knee flexion $> 100^\circ$ or $\leq 100^\circ$), a Generalised Estimating Equation model will be
728 used to test the treatment effect, with the adjustment of the covariates as above.

729 For the sensitivity analysis, we will also perform a per protocol analysis including only
730 patients who complied with the treatment protocol. Compliance for HI group will be defined
731 as attendance of a minimum of 7 days of inpatient rehabilitation, along with attendance at no
732 less than two outpatient sessions and no more than five. Compliance for the HO group will be
733 defined as attendance at no less than two outpatient sessions and no more than five.

734 There will be procedures put in place to minimise loss to follow-up, such as obtaining
735 multiple contact details at time of consent and reminders that assessments are due. The age,
736 gender and height of participants will be used as stratification variables in the randomisation
737 procedure via a minimisation algorithm. The mixed model analysis indicated above will
738 include these three variables as additional covariates to incorporate the possible within
739 treatment group correlation associated with by stratification [3].

740 For the analyses involving the observational arm, the change score in the primary outcome
741 will be compared between the observational group and those in the randomised home group
742 adjusting for other covariates. A lack of significant difference in scores between the two
743 groups will suggest there is no strong preference effect in this trial and we may not need to
744 include preference as a covariate in the RCT analyses. To be consistent with the two RCT
745 groups, we will aim for a minimum 64 participants in the observational group.

746 Cost-effectiveness analysis will be undertaken if the inpatient arm is shown to be superior.
747 Due to limited funding, we will no longer utilize data from the PBS or Medicare. Costs will
748 be based on standardized unit prices and based on patient diaries of expenses.

749

750

751 **References**

- 752 1. Sterne J, White I, Carlin J et al: Multiple imputation for missing data in epidemiological
753 and clinical research: potential and pitfalls. *BMJ* 2009; 338: b2393.
- 754 2. Donders R, van der Heijden G, Stijnen T, Moons K: Review: A gentle introduction to
755 imputation of missing values. *J Clin Epi* 2006 59: 1087e-1091.

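### Protocol and SAP state different age cut-points for the minimisation (70 v 68 years), and recruiting site is in neither the minimisation nor any named covariate list

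*Supplement*

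**What the plan says.** **Allocation rule.** Protocol version 5 (16 January 2014), section 5.6, specifies "minimisation stratified for age" and two further factors; the full phrase is "minimisation stratified for age (≤ 70 , >70 y), gender and height". It gives no cut for height. The SAP (January 2014), Background, says the factors were chosen "for variables that affect the primary outcome (distance walked in the 6MWT - age (≤ 68 y" and continues ">68 y), height (≤ 163 cm, >163 cm), and gender". Both texts describe one central telephone randomisation service with 1:1 allocation.

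**Site.** Protocol section 3.4 states: "There are two recruitment centres and four treatment sites". Fairfield and Sutherland recruit, Braeside and Sutherland provide the inpatient stay, and Fairfield, Sutherland and Campbelltown oversee the home programme. The SAP, under Outcome measures, mentions the change ("With the addition of a second recruitment site, the definitive sample is expected to" reach about 160), but only in connection with sample size and power.

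**Models (SAP, Analyses subsets).**
- Primary ANCOVA: treatment, baseline walking distance, weight, co-morbidities and patient preference.
- Mixed model: baseline value of the outcome, with weight, co-morbidities and preference given as examples of further factors. A later paragraph says the age, "gender and height of participants will be used as stratification variables in the randomisation" procedure, and adds these three to the mixed model.
- GEE for knee flexion: the covariates already listed.

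Site is named in none of these.

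**The concern.** There are two separate issues.

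First, a single service runs a single algorithm, so it cannot cut age at both 70 and 68 years. The trial report has to describe the allocation rule, and a reader cannot tell from these documents which description is true. The SAP says the factors were picked because they affect walking distance, so the rule is part of the design rationale.

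Second, a second recruiting hospital with its own inpatient unit has joined the trial. Walking distance may differ between hospitals through case-mix or test conditions. With site absent from both the minimisation and the models, a chance imbalance in site between the arms is left uncorrected, and any between-site variance stays in the residual. A plan silent on site also leaves room to choose later between site-adjusted and unadjusted results.

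**Working it through.** **1. Cut-points side by side.**

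| Factor | Protocol 5.6 | SAP, Background | Status |
|---|---|---|---|
| Age | 70 y | 68 y | Contradiction |
| Height | listed, no cut | 163 cm | Added detail |
| Gender | listed | listed | Agree |
| Recruiting site | not listed | not listed | Absent from both |

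Patients older than 68 and up to 70 fall in different age strata under the two rules.

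**2. The plan's own sample size.** Inputs from the SAP: difference 60 m (400 v 460 m), SD 120 m, 5% significance (taken as two-sided), 80% power, loss under 10%.

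n per arm = 2 × (1.960 + 0.842)² × (120/60)² = 62.8, so 63. Allowing for 10% loss, 63/0.9 = 70 per arm, 140 in total. The plan's figure is reproduced.

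Standard error of the treatment difference without covariates = 120 × √(2/63) = 21.4 m.

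**3. Shift from one chance imbalance.** The documents give neither the second site's share nor the difference between sites. Assume 35 of 140 patients come from the second site and sites differ by 30 to 50 m.

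- A 22:13 split or worse between arms has probability 0.175 if each patient is allocated independently (binomial, 35 patients, 0.5). With arm totals fixed at 70:70 it is 0.118 (hypergeometric).
- That split differs by 9 patients, 9/70 = 12.9 percentage points of site mix.
- Shift with no baseline adjustment: 9/70 × 30 to 50 m = 3.9 to 6.4 m.
- The planned ANCOVA adjusts for baseline distance. If the same site gap exists at baseline and the baseline slope is 0.5 to 0.7 (assumed), a fraction 0.3 to 0.5 of the shift remains: 3.9 × 0.3 = 1.2 m up to 6.4 × 0.5 = 3.2 m.
- With the roughly 160 participants the SAP expects, the same nine-patient difference gives 9/80 × 30 to 50 m = 3.4 to 5.6 m before baseline adjustment.

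**4. Wider range.** Let p be the second site's share (0.2 to 0.5) and D the site difference (20 to 60 m), both assumed, with 63 per arm.

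- 95% range of the chance difference in site share: ±1.96 × √(2p(1−p)/63) = ±14.0 points (p = 0.2) to ±17.5 points (p = 0.5).
- Shift before baseline adjustment, that range × D: ±2.8 m (p = 0.2, D = 20) to ±10.5 m (p = 0.5, D = 60).

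**5. Precision.** Within-site SD = √(120² − p(1−p)D²), which is 119.7 m at p = 0.2, D = 20 and 116.2 m at p = 0.5, D = 60. Power at 63 per arm rises from 80.1% to 80.3% and 82.6% respectively, a gain of 0.2 to 2.5 points.

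**The case against.** The case against giving this much weight has several parts.

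- **Misclassified patients.** A reader might infer that the wrong cut-point would corrupt the analysis. The documents do not support that. The primary ANCOVA as written contains neither age nor height, and the mixed model takes them as covariates without saying that they are dichotomised. The contradiction concerns the documented allocation rule. This objection stands.
- **Height.** A reader might count the missing protocol cut as a second contradiction. It is not: the SAP supplies a detail on which the protocol is silent.
- **Bias.** A reader might infer that omitting site biases the result. Under randomisation the imbalance has mean zero, and the confidence interval already allows for it. A shift of 3.9 to 6.4 m is 0.18 to 0.30 of the 21.4 m standard error, and the planned baseline adjustment would absorb part of it. This stands, and it makes the site point modest.
- **Open wording.** The mixed-model covariates are introduced as examples, so site could be added. That is true, but the ANCOVA list is closed, and a plan should not leave site to inference.
- **Incomplete remedy.** Assessments take place at Fairfield, Sutherland or Campbelltown, occasionally at home, under standardised protocols with blinded assessors. A two-level recruiting-site term would not capture all variation in assessment location. This stands as a limit on what the term achieves, but it is no reason to omit the term.

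**Conclusion.** Both parts hold on the text. The age cut-points contradict each other in two current documents of the same month, and nothing in either shows which one the randomisation service uses. It cannot be inferred that allocation was carried out wrongly, only that at least one description of it is wrong.

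The omission of recruiting site is a missed opportunity for precision and for protection against chance imbalance. It is not a source of systematic error. The likely consequence is a few metres on a 60 m target and at most about 2.5 points of power. Those sizes rest entirely on assumed site shares, site differences and a baseline slope; the documents give none of them. The point is worth acting on because the remedy is cheap, not because the effect is large.

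**What to change.** 1. Obtain the cut-points held by the randomisation service and correct whichever document disagrees. State the height cut in both.
2. Prespecify recruiting site (Fairfield or Sutherland) as a two-level covariate in the primary ANCOVA, the mixed model and the GEE.
3. State that age and height enter as continuous covariates, together with gender, in the primary ANCOVA as well as the mixed model. The model results then do not depend on either cut-point, and the primary analysis reflects the minimisation factors.
4. Leave the running minimisation and the sample size unchanged.

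The cost is SAP wording, one check with the service and a few degrees of freedom: one for site in each model, and three more in the ANCOVA for age, height and gender. Recruiting hospital, age, height and gender should already be known for every randomised patient, so no new data collection is expected.

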663 (The HIHO study): study protocol for a randomized controlled trial. *Trials* 2013; 14:432.

664 The study was registered prospectively in April 2012 on a clinical trials registry - U.S.
665 National Institutes of Health Clinical Trials Registry ref: NCT01583153.

666 **eMethods1. Statistical analysis plan**

667

668 **HIHO STATISTICAL ANALYTICAL PLAN (SAP) – JANUARY 2014**

669

670 **Background**

671 HIHO is a 2-armed parallel randomised controlled trial comparing 10 days on inpatient
672 rehabilitation followed by a hybrid home program (usual care) to a hybrid program alone in
673 people who have undergone a TKA. A third observational arm provides the opportunity to
674 assess the effect of preference on the measured outcomes as well as assess generalisability of
675 the randomised cohort.

676 Participants are randomly assigned via a central randomisation process to 1 of 2 arms. A
677 centralised randomisation service will be used for participant randomisation using a 1:1 ratio,
678 providing secure, coded randomisation via telephone. Group allocation, therefore, will be
679 concealed from all parties until the result of the randomisation is known. Participants will be
680 randomised to one of the two intervention groups using the method of minimisation stratified
681 for variables that affect the primary outcome (distance walked in the 6MWT - age (≤ 68 y,
682 >68 y), height (≤ 163 cm, >163 cm), and gender.

683 Participants are followed up by an assessor blind to treatment allocation at 10, 26 and 52
684 weeks.

685 Neither therapists or participants are blind to the intervention received.

686 Different therapists are involved in the delivery of the inpatient and home-based programs.

687 **Data management**

688 Data will be sent by blinded assessors to blinded data entry staff for collation and data entry,
689 with range checks for data values. All databases will be password protected and stored in
690 secure areas. Data will be checked for accuracy against the source documents by the study
691 coordinator after all participants are randomized and then when all participants have had their
692 final follow-up.

693 **Statistical plan**

694 **Outcome measures:** The primary outcome and most secondary outcomes will be measured
695 pre-operatively, at week 10 (the time when the home program formally ceases), and then at 6
696 and 12 months post-randomisation. Assessments will be performed by an observer blinded to
697 the participants' study allocation.

698 The primary endpoint in this trial is functional mobility at 6 months post-surgery measured
699 using the distance walked during a 6MWT. Seventy participants in each group (140 in total)
700 will provide 80% power at a significance level of 5%, to detect an increase in walking
701 capacity from 400 m to 460 m between the Home and Inpatient groups respectively in the
702 six-minute walk test at six months post-surgery, assuming a SD of 120 m and a drop-out rate
703 of $< 10\%$. With the addition of a second recruitment site, the definitive sample is expected to
704 be approximately 160 participants, allowing us to increase the power of the study.

705 In the absence of data describing the minimum clinically important difference (MCID) for the
706 6MWT, a sub-study is now included to evaluate the MCID/MID for measured mobility in
707 this population.

708 **Descriptive analyses at baseline**

709 Comparability of intervention groups will be investigated at baseline. Descriptive statistics
710 will be presented, including summary statistics of potential confounding variables.

711 **Analyses subsets**

712 Data analysis will be completed using the principle of intention-to-treat (ITT) [1]. We will
713 include all randomised participants regardless of level of compliance with the protocol. The
714 primary outcome variable is distance measured using the outcome of a 6MWT at 26 weeks.

715 Analysis of covariance will be used for this primary outcome, with treatment group as the
716 main study factor and walking distance at baseline, weight, co-morbidities and patient
717 preference as covariates. For participants with a missing outcome measure at 26 weeks, an
718 imputation method will be used [1,2].

719 The secondary outcome variables include the 6MWT at 10 and 52 weeks post-surgery, the 15
720 metre walk test, EQ5D, Oxford Knee Score, KOOS and knee ROM at most post-surgery time
721 points.

722 Mixed model analyses will be used for the continuous variables measured repeatedly at 10,
723 26 and 52 weeks to estimate the treatment group by time effects. These analyses incorporate
724 the missing data that may occur at the follow up occasions. Baseline measurements of the
725 outcome variables, together with factors, such as weight, co-morbidities and patient
726 preference, will be included as covariates. For the binary outcome measured 10, 26 and 52
727 weeks (knee flexion $> 100^\circ$ or $\leq 100^\circ$), a Generalised Estimating Equation model will be
728 used to test the treatment effect, with the adjustment of the covariates as above.

729 For the sensitivity analysis, we will also perform a per protocol analysis including only
730 patients who complied with the treatment protocol. Compliance for HI group will be defined
731 as attendance of a minimum of 7 days of inpatient rehabilitation, along with attendance at no
732 less than two outpatient sessions and no more than five. Compliance for the HO group will be
733 defined as attendance at no less than two outpatient sessions and no more than five.

734 There will be procedures put in place to minimise loss to follow-up, such as obtaining
735 multiple contact details at time of consent and reminders that assessments are due. The age,
736 gender and height of participants will be used as stratification variables in the randomisation
737 procedure via a minimisation algorithm. The mixed model analysis indicated above will
738 include these three variables as additional covariates to incorporate the possible within
739 treatment group correlation associated with by stratification [3].

740 For the analyses involving the observational arm, the change score in the primary outcome
741 will be compared between the observational group and those in the randomised home group
742 adjusting for other covariates. A lack of significant difference in scores between the two
743 groups will suggest there is no strong preference effect in this trial and we may not need to
744 include preference as a covariate in the RCT analyses. To be consistent with the two RCT
745 groups, we will aim for a minimum 64 participants in the observational group.

746 Cost-effectiveness analysis will be undertaken if the inpatient arm is shown to be superior.
747 Due to limited funding, we will no longer utilize data from the PBS or Medicare. Costs will
748 be based on standardized unit prices and based on patient diaries of expenses.

749

750

751 **References**

- 752 1. Sterne J, White I, Carlin J et al: Multiple imputation for missing data in epidemiological
753 and clinical research: potential and pitfalls. *BMJ* 2009; 338: b2393.
- 754 2. Donders R, van der Heijden G, Stijnen T, Moons K: Review: A gentle introduction to
755 imputation of missing values. *J Clin Epi* 2006 59: 1087e-1091.
